Official title: Treatment of acute exacerbations of chronic obstructive pulmonary disease with acupuncture during hospitalization: a three-arm double-blinded randomized sham-controlled trial

NCT number: NCT03398213

Date of the document: June 3, 2020

Methods:

Study design: This is a three-arm 1:1:1 randomized-controlled trial evaluating the efficacy and safety of the addition of acupuncture to SOC as compared to sham-procedure added to SOC (sham-control) and to SOC only (SOC-control) for treatment of AECOPD in patients hospitalized in internal medicine departments. The study protocol was reviewed and approved by the Institutional Review Board (IRB) in accordance with the Helsinki Declaration (0108-17-BNZ) and registered at www.clinicaltrials.gov (NCT03398213). Trial methods and results were reported according to the Consolidated Standards of Reporting Trials (CONSORT) 2010 guidelines.¹⁹

Participants: Patients hospitalized in internal medicine departments with a previous diagnosis of COPD³ were evaluated by department physicians. Inclusion criteria included a previous diagnosis of COPD and a clinical diagnosis of AECOPD as defined by the GOLD criteria.³ Exclusion criteria included hemodynamic instability, a platelet count below $20 \times 10^9/L$, expected respiratory deterioration requiring mechanical ventilation in the next 24 hours, or an inability to provide informed consent. Primary socio-demographic and medical data were recorded and compared between the three study groups.

Setting: The study was set in internal medicine departments of Bnai Zion medical center, a tertiary hospital in Haifa, Israel.

Interventions: The intervention protocol was based on a literature review and the Delphi process. A panel of eight acupuncturists of at least 5 years of experience in treating hospitalized patients were consulted. The experts were asked to review and analyze the literature regarding Traditional Chinese Medicine (TCM) and COPD, delineate relevant TCM syndromes and associated "critical" acupoints and treatment frequency. Their suggestions were based on literature data and their professional experience. Finally, three cycles of stepwise anonymous discussions were taken to obtain a consensus on the treatment approach. The conclusion was to

assign the patients into three groups for four daily consecutive treatment sessions and a 4-day follow-up.

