Statistical analysis: Demographic and clinical data was analyzed at baseline to measure the balance among the study groups. Quantitative variables were described using mean \pm standard deviation or median and 25th-75th percentiles (Q1, Q3) depending on their distribution. Qualitative variables were described using frequency and percentage distributions. Next, we showed that our variables distribute equally between the study groups. For comparing normally distributed variables between our study groups, we used the ANOVA test. For comparing variables that do not distribute normally between our study groups, we used the Kruskal-Wallis test with adaptation to pairwise comparison. For comparing qualitative variables between our study groups, we used the independent Chi-square test and Fisher exact test. Bonferroni adjustment was used for multiple comparisons for each independent comparison of true acupuncture vs sham-control, true acupuncture vs SOC-control and sham-control vs SOC-control. Since the variation of dyspnea intensity between day 1 and day 2 had a normal distribution, a multivariate linear regression analysis was performed after collinearity, interaction and confounding analysis, in order to neutralize the effect of the different sociodemographic and medical covariates on the primary outcome in the 3 study arms. The adjusted unstandardized regression coefficients were given with confidence interval (CI), while

a $p < 0.05$ was considered as statistically significant. Data analysis was performed using IBM SPSS version 22 statistics software.

Results:

Baseline patient data: 104 patients were screened for eligibility from November 2017 to February 2020. Among them, 72 met inclusion criteria and were recruited. Twenty-six of them were assigned to the true acupuncture arm, 24 to the sham-control arm, and 22 to the SOC-control arm. Baseline demographic and clinical characteristics were similar in patients from the 3 study arms as shown in Table 1. To note, all the patients randomized to any of the three groups completed treatments per-protocol (Fig. 1).

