Primary outcome: Baseline dyspnea was similar in the three groups. A statistically significant difference between the three groups in dyspnea intensity was found from the first day of evaluation after treatment (median [Q1, Q3] mBorg score 5.0 [4.0, 5.0] in true acupuncture, 6.0 [4.25, 7.875] in sham-control and 7.5 [5.5, 8.0] in SOC-control, $p=0.014$ – significant difference of both true acupuncture vs sham-control: $p=0.031$, and true acupuncture vs SOC-control: $p=0.014$, but non-significant between sham-control and SOC-control: $p=0.34$), and until day 3 after treatment (Fig. 2A). After adjustment for such covariates in a multivariate linear regression analysis, the association of study arm with improvement of dyspnea from day 1 to day 2 remained statistically significant (Table 2).

Secondary outcomes:

- Patient-reported outcomes:

Baseline VAS scores for cough and sputum intensity were similar in the three study arms (Table 1). No statistically significant difference in the cough intensity was observed between the three study arms throughout the 4 days of follow-up (Fig. 2). However, a statistically lower level of sputum production was observed in the true acupuncture arm as compared with sham-control and SOC-control from day 2 ($p=0.04$) (Fig. 2). Post-hoc analysis showed a statistically significant difference between true acupuncture and sham-control in day 2 ($p=0.024$), day 3 ($p=0.010$) and day 4 ($p=0.018$), while only on day 2 between true acupuncture and SOC-control ($p=0.044$), and no statistically significance between sham-control and SOC-control.

- Physiologic assessment:

Baseline physiologic data were similar in the three groups (Table 1). A statistically significant difference was observed in respiratory rate (RR) at day 2 after treatment ($p=0.002$), with significant difference both between true acupuncture and sham-control ($p=0.005$) and between true acupuncture and SOC-control ($p=0.003$), but not between sham-control and SOC-control

($p=0.050$), while all other RR measurements were statistically similar between the 3 arms throughout the 4-day follow-up (Fig. 3A).

Concerning pH, a statistically significant difference was observed at day 4 between the 3 groups ($p=0.048$), although post-hoc analysis did not show any statistical significance when comparing groups head-to-head (Fig. 3C).

No statistically significant difference was observed when comparing other physiologic measures between the 3 study groups (Fig. 3).

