- *Treatment failure:*

No death or mechanical ventilation occurred in the study participants during follow-up. However there had a total of 4 treatment failures, all of them were non-invasive ventilations, which occurred in 2 (8%) patients in the true acupuncture arm, 1 (4.3%) in the sham-control arm and 1 (5%) in the SOC-control arm ($p=0.83$).

- *Duration of hospitalization:*

No difference was noted in terms of duration of hospitalization between the three study arms (5.5 ± 2.3 days for true acupuncture vs. 6.0 ± 2.9 days for sham-control and 6.3 ± 2.9 days for SOC-control, $p=0.050$).

- *Safety:*

No side effect of acupuncture treatment was reported during the study period as assessed by the Acup-AE questionnaire.

Tables and Figures:

Table 1: Baseline characteristics

[figure not shown]
Characteristics	True acupuncture (N=26)	Sham-control (N=24)	SOC-control (N=22)	p
Age (mean ± SD)	69.2±10.1	70.7±8.1	67.4±9.3	0.47
Gender (Men)	20 (77%)	15 (62%)	17 (77%)	0.43
Comorbidities				
Cardiovascular	18 (69%)	20 (83%)	15 (68%)	0.42
Respiratory (other than COPD)	7 (27%)	2 (8%)	5 (23%)	0.23
Gastroenterological	2 (8%)	4 (17%)	5 (23%)	0.34
Renal / Urologic	7 (27%)	3 (12%)	5 (23%)	0.44
Metabolic / Endocrinological	15 (58%)	13 (54%)	13 (59%)	0.94
Hematological / Oncological	3 (12%)	6 (25%)	3 (14%)	0.40
Neurological	4 (15%)	0 (0%)	1 (5%)	0.09
Smoking status				
Smoker	13 (50%)	16 (67%)	14 (64%)	0.44
Former smoker	13 (50%)	8 (33%)	8 (36%)	
Never smoked	0	0	0	
CCI (median [Q1, Q3])	6.0 [3.5, 6.0]	5.0 [4.0, 6.75]	4.5 [3.0, 7.25]	0.87
COPD severity				
Mild: FEV1 ≥ 80%	1 (4%)	0 (0%)	1 (5%)	
Moderate: 50% ≤ FEV1 < 80%	4 (15%)	5 (21%)	5 (23%)	0.69
Severe: 30% ≤ FEV1 < 50%	7 (27%)	11 (46%)	9 (41%)	
Very severe: FEV1 < 30%	5 (19%)	4 (17%)	4 (18%)	
Unknown	9 (35%)	4 (17%)	3 (14%)	
Pulmonary hypertension				
None	10 (38%)	15 (62%)	16 (73%)	
Mild: mPAP = 25-40 mmHg	4 (15%)	3 (12%)	3 (14%)	
Moderate: mPAP = 41-55 mmHg	3 (12%)	0	2 (9%)	0.11
Severe: mPAP > 55 mmHg	0	0	0	
Unknown	9 (35%)	6 (25%)	1 (5%)	
COPD exacerbation hospitalizations				
0	19 (73%)	12 (50%)	9 (41%)	
1-4	6 (23%)	11 (46%)	9 (41%)	0.09
≥5	1 (4%)	1 (4%)	4 (18%)	
Treatment				
Inhalations	24 (92%)	23 (96%)	22 (100%)	0.41
Systemic corticosteroids	3 (12%)	3 (13%)	1 (5%)	0.61
Theophylline	0	0	1 (5%)	0.32
Oxygen home therapy	8 (31%)	12 (52%)	8 (36%)	0.29
BiPAP	4 (15%)	2 (8%)	4 (18%)	0.60
APACHE-II at admission (mean ± SD)	13.3±3.6	12.0±4.4	11.0±3.8	0.14
Baseline data (median [Q1, Q3])				

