Dyspnea (mBorg)	8.0 [5.5, 8.75]	6.5 [5.0, 8.5]	7.75 [6.0, 8.5]	0.82
Cough (VAS)	7.5 [5.0, 8.0]	5.0 [5.0, 7.4]	5.0 [3.6, 7.5]	0.35
Sputum (VAS)	6.0 [1.5, 7.5]	6.0 [4.25, 6.0]	5.0 [1.9, 6.0]	0.22
O₂ saturation				
≤ 80%	4 (15%)	1 (4%)	0	0.30
81-89%	9 (35%)	10 (42%)	10 (45%)	
≥ 90%	13 (50%)	13 (54%)	12 (55%)	
PCO₂ (mmHg)				
< 45	6 (23%)	3 (12%)	8 (36%)	
45-60	12 (46%)	17 (71%)	9 (41%)	0.10
60-80	5 (19%)	4 (17%)	5 (23%)	
> 80	3 (12%)	0	0	
pH				
< 7.2	0	0	0	
7.2-7.3	5 (19%)	4 (17%)	1 (5%)	0.30
> 7.3	21 (81%)	20 (83%)	21 (95%)	
Respiratory rate (/min) (median [Q1, Q3])	21 [16, 23.75]	22 [16.5, 26]	20 [16, 22]	0.26

Legend: CCI: Charlson Comorbidity Index; mPAP: Mean Pulmonary Arterial Pressure; SOC: Standard-Of-Care.

Table 2: Multivariate linear regression analysis on variation of dyspnea from day 1 to day 2

Factors and covariates	Adjusted unstandardized coefficient (B)	95% Confidence interval		p value
		Inferior	Superior	
Constant (Intercept)	2.088	-3.409	7.584	0.457
Study Arm				
True acupuncture	2.172	0.421	3.923	0.015
Sham-control	0.390	-1.319	2.099	0.655
SOC-control	0	-	-	-
Cardiovascular comorbidities (0=No, 1=Yes)	-0.322	-2.935	1.391	0.713
Gastroenterological comorbidities (0=No, 1=Yes)	4.703	2.527	6.879	<0.001
Hospitalizations for COPD in the last year	-0.379	-0.756	-0.003	0.048
Age	-0.040	-0.133	0.053	0.400
APACHE-II	0.118	-0.099	0.336	0.287
Charlson Comorbidity Index	-0.026	-0.406	0.354	0.894

Figure 1: Flow-chart

Legend: SOC: Standard-of-care.

Figure 2: Between-group comparison of patient-reported outcomes

[figure not shown]

Figure 3: Between-group comparison of physiologic features

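### Table 2 prints no adjusted acupuncture-versus-sham contrast and no overall arm test, and the sputum day 2 pairwise p-values look unadjusted despite the stated Bonferroni rule

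*Combined protocol and SAP*

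**What the plan says.** The Study design section describes a trial "evaluating the efficacy and safety of the addition of acupuncture to SOC as compared to sham-procedure added to SOC (sham-control") and also to SOC alone, so both controls have equal standing.

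The Statistical analysis section says "Bonferroni adjustment was used for multiple comparisons for each independent comparison of true acupuncture vs sham-control, true acupuncture vs SOC-control" and for sham versus SOC. It names Kruskal-Wallis for non-normal variables but does not name the pairwise test that follows it. It describes a linear regression for the day 1 to day 2 change in dyspnea and sets 0.05 as the significance level. It does not say whether Bonferroni extends to the arm contrasts in that regression.

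Under Results, Primary outcome, the text states that "the association of study arm with improvement of dyspnea from day 1 to day 2 remained statistically significant (Table 2"). The cited table is headed "Table 2: Multivariate linear regression analysis on variation of dyspnea from day 1 to day 2". Its arm rows are:

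- True acupuncture: 2.172, 95% CI 0.421 to 3.923, p=0.015
- Sham-control: 0.390, 95% CI −1.319 to 2.099, p=0.655
- SOC-control: reference, 0

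Under Patient-reported outcomes, sputum is said to be lower with acupuncture "as compared with sham-control and SOC-control from day 2 ($p=0.04"). The text continues: "Post-hoc analysis showed a statistically significant difference between true acupuncture and sham-control in day 2 ($p=0.024"), and then "while only on day 2 between true acupuncture and SOC-control ($p=0.044").

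**The concern.** There are two separate problems.

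(a) The sentence on the adjusted analysis makes a statement about study arm as a factor, but the table it cites contains no test of that factor. What the table shows is acupuncture against SOC. The contrast with sham, which separates needling from the attention and expectation that come with a procedure, is missing from the only covariate-adjusted analysis of the primary outcome. A reader could take the sentence to cover both controls.

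(b) If the sputum day 2 pairwise values are unadjusted, the reported significance does not follow the multiplicity rule that the document says it used, and both differences claimed for that day disappear under the rule. It also leaves open which basis applies to the other pairwise p-values, including dyspnea on day 1 against sham (p=0.031).

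**Working it through.** **(a) Adjusted acupuncture versus sham**

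*Reproducing Table 2.* SE = CI width / (2 × 1.96).

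- Acupuncture: (3.923 − 0.421)/3.92 = 0.893; z = 2.172/0.893 = 2.43; two-sided normal p = 0.015, as printed.
- Sham: (2.099 + 1.319)/3.92 = 0.872; z = 0.390/0.872 = 0.447; p = 0.655, as printed.

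Both intervals are centred on their coefficients, so these SEs are usable.

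*The missing contrast.* Difference = 2.172 − 0.390 = 1.782. Its variance is 0.893² + 0.872² − 2r(0.893)(0.872), where r is the correlation of the two coefficients. r is not printed and has to be assumed. Arm sizes alone (26/24/22, ignoring covariates) give r = (1/22)/√[(1/26+1/22)(1/24+1/22)] = 0.53, and also 0.53 with 23 sham patients.

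*Overall arm test.* Wald chi-square on 2 df = (z₁² + z₂² − 2r z₁z₂)/(1 − r²). At r = 0.53 it is (5.911 + 0.200 − 1.153)/0.719 = 6.90, so p = exp(−6.90/2) = 0.032.

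| r | SE | 95% CI | p vs sham | p × 3 | overall arm p |
|---|---|---|---|---|---|
| 0.3 | 1.045 | −0.27 to 3.83 | 0.088 | 0.264 | 0.050 |
| 0.4 | 0.967 | −0.11 to 3.68 | 0.065 | 0.196 | 0.044 |
| 0.5 | 0.883 | 0.05 to 3.51 | 0.044 | 0.131 | 0.035 |
| 0.53 | 0.856 | 0.10 to 3.46 | 0.037 | 0.112 | 0.032 |
| 0.6 | 0.790 | 0.23 to 3.33 | 0.024 | 0.072 | 0.023 |
| 0.7 | 0.684 | 0.44 to 3.12 | 0.009 | 0.028 | 0.011 |

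The contrast crosses 0.05 at r of about 0.47, and its Bonferroni value crosses at about 0.64. Acupuncture against SOC is 0.015 × 3 = 0.045 if Bonferroni applies.

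**(b) Sputum day 2**

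*Inputs.* Overall p=0.04 (0.035 to 0.045 with rounding); pairs 0.024 and 0.044; arms 26/24/22, assuming that everyone was analysed.

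*Dunn tests after Kruskal-Wallis.* The two pairwise z-scores share the acupuncture arm, so their correlation is (1/26)/√[(1/26+1/24)(1/26+1/22)] = 0.469, and H = (z₁² + z₂² − 2(0.469)z₁z₂)/(1 − 0.469²).

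- Read as unadjusted: z = 2.257 and 2.014, H = 6.27, overall p = 0.044. This prints as 0.04.
- Read as Bonferroni-adjusted (p/3 = 0.008 and 0.0147): z = 2.652 and 2.441, H = 8.87, overall p = 0.012. This does not.

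Arms of 26/23/22 or 25/23/20 give 0.043 and 0.012. The smaller sizes allow for missing patients: under Treatment failure, "1 (4.3%) in the sham-control arm and 1 (5%) in the SOC-control arm" implies a sham denominator of 23.

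*Bound free of arm sizes.* No Dunn |z| can exceed √H. Overall p=0.04 means H = 6.44 and |z| ≤ 2.537, so the smallest possible adjusted p is 0.034 (0.029 if the overall p were 0.035). An adjusted 0.024 is not attainable.

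*Other pairwise tests.* Pooled-variance t-tests after ANOVA give 0.044 unadjusted and 0.012 adjusted. Separate two-group rank tests were simulated (389,272 draws; normal and skewed scores from 0 to 10 in half points; equal and unequal spread; pairs matched within about 25%). Read as unadjusted, the median overall p was 0.040 (95% range 0.030 to 0.050; 799 matches). Read as adjusted, the median was 0.011 and the maximum 0.015, and none of 653 matches reached 0.035. In a second simulation, none of 2,258 data sets with an overall p of 0.035 to 0.045 had adjusted pairs as low as 0.024 and 0.044.

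*Applying the stated rule.* 0.024 × 3 = 0.072 against sham and 0.044 × 3 = 0.132 against SOC. If Bonferroni instead meant a lowered threshold of 0.05/3 = 0.0167, neither value meets it.

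*Conditional only, if the other values are also unadjusted.* Sputum against sham: 0.030 on day 3 and 0.054 on day 4. Dyspnea day 1: 0.093 against sham and 0.042 against SOC.

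**The case against.** On (a), the Results sentence names no comparator, and the overall arm test is probably significant, so the sentence is probably true. The Results also print a day 1 dyspnea comparison with sham (p=0.031), though without covariate adjustment. The 0.05 level stands in the same sentence as the regression coefficients, so the regression may have been meant to stand outside Bonferroni. The range 0.3 to 0.7 for the correlation is wide: simulating the design from the Table 1 distributions (with assumed covariate independence and spreads) gives a median of 0.56 and a 95% range of 0.50 to 0.62. All of this is fair. At 0.50 and 0.62 the contrast p is 0.044 and 0.021, so before multiplicity adjustment it is more likely below 0.05 than not. Times 3, however, the two values are about 0.13 and 0.06, so the unanswered Bonferroni question decides the reading. None of this puts the contrast in the table.

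On (b), the Dunn check does not fit the other printed sets. Dyspnea day 1 implies an overall p of 0.026 or 0.007 against a printed 0.014, and respiratory rate day 2 implies 0.0034 or 0.0009 against 0.002. Dunn was therefore probably not the test used, and the sputum match on Dunn alone would be thin. The t-test and two-group rank-test results give the same split, so the conclusion does not depend on Dunn. The overall p is given to only two decimals, but the rounding range is allowed for above. The 5% in SOC-control fits any denominator from 19 to 22, so 25/23/20 is only a sensitivity case; it changes nothing. A misprint cannot be excluded: the hospital-stay p of 0.050 does not follow from the printed means and SDs, which give about 0.58. That is a reason to check the output rather than to leave the values unlabelled.

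The inconsistency is shown for one secondary outcome on one day. The pH result on day 4 (overall significant, no significant pair) is compatible with adjustment having been applied there.

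**Conclusion.** Both parts hold, at medium confidence overall.

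(a) The omission is read directly from Table 2. The adjusted estimate against sham is 1.78 points. Its p-value is 0.037 under the arm-size correlation but cannot be recovered from the document, and the answer can change with the correlation and with whether Bonferroni applies. This is a gap in reporting; it does not show that acupuncture fails against sham.

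(b) The printed sputum day 2 set fits unadjusted pairwise values and conflicts with the stated Bonferroni rule. Under that rule both claimed differences lose significance (0.072 and 0.132). This is an inference from printed p-values, assuming two-sided tests and roughly full arms; it holds under each of the three pairwise methods examined. For dyspnea day 1 and the other outcomes the text does not settle which basis was used.

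**What to change.** From the same model and data:

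1. Add to Table 2 the acupuncture-minus-sham contrast with its confidence interval and p-value, and a 2-df test of arm.
2. State whether Bonferroni covers the regression contrasts.
3. Name the pairwise test, recompute every pairwise p-value with the stated adjustment, and label the values as adjusted.
4. Revise the significance statements in the Results wherever one changes, starting with sputum day 2.
5. While reprinting Table 2, check the cardiovascular row: its interval (−2.935 to 1.391) has midpoint −0.772, but the coefficient is −0.322.

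The cost is re-running existing output. The price is that some stated results may become less favourable.

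### The sputum summary claims a difference from both controls from day 2 on, but the post-hoc tests show a difference from SOC-control on day 2 only

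*Combined protocol and SAP*

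**What the plan says.** In the combined protocol and SAP, under Results, secondary outcomes, patient-reported outcomes, the sputum result comes in two steps.

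- **Summary sentence.** Sputum was statistically lower in the true acupuncture arm "as compared with sham-control and SOC-control from day 2", with p=0.04.
- **Post-hoc sentence, directly after it.** True acupuncture differed from sham-control on day 2 (p=0.024), day 3 (p=0.010) and day 4 (p=0.018), "while only on day 2 between true acupuncture and SOC-control" (p=0.044), and there was "no statistically significance between sham-control and SOC-control".

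Three statements under Statistical analysis bear on this. For variables that are not normally distributed, "we used the Kruskal-Wallis test with adaptation to pairwise comparison". A Bonferroni adjustment is said to cover the three pairs of arms. On significance, "a $p < 0.05$ was considered as statistically significant". Nothing there or in the Results says whether the printed pairwise p-values are before or after adjustment.

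**The concern.** The summary sentence gives a direction, names both controls and sets a starting day. Symptoms were assessed over four days, so its natural reading is that acupuncture beat each control on days 2, 3 and 4. A three-group test cannot carry that statement: it has no direction and does not identify which arms differ. Only the pairwise tests can, and they do not go that far for SOC-control.

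The study design section sets acupuncture plus SOC against both sham plus SOC and SOC alone, so the SOC-control contrast is one of the trial's stated questions. Someone who lifts the summary sentence would report a sustained sputum benefit over standard care that the trial's own tests do not show. If the printed pairwise values are unadjusted, even the single day on which a difference from SOC-control is reported would not meet the stated criterion.

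**Working it through.** **Step 1. Set the two sentences side by side.** The count of six contrasts (two controls by three days) is my reading of the summary sentence; the document does not list them.

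| Contrast | Summary sentence | Post-hoc sentence |
|---|---|---|
| vs sham-control, day 2 | lower | p=0.024 |
| vs sham-control, day 3 | lower | p=0.010 |
| vs sham-control, day 4 | lower | p=0.018 |
| vs SOC-control, day 2 | lower | p=0.044 |
| vs SOC-control, day 3 | lower | not significant; no value in the text |
| vs SOC-control, day 4 | lower | not significant; no value in the text |

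Four of the six are reported as significant. The two that are not are both against SOC-control.

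**Step 2. Apply the stated Bonferroni adjustment.** With three pairs, adjusted p = 3 × raw p, compared with 0.05. This applies only if the printed values are raw.

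- sham-control, day 2: 3 × 0.024 = 0.072
- sham-control, day 3: 3 × 0.010 = 0.030
- sham-control, day 4: 3 × 0.018 = 0.054
- SOC-control, day 2: 3 × 0.044 = 0.132

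Only sham-control on day 3 stays below 0.05.

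**Step 3. Are the printed values raw or adjusted?** The text has no daily sputum scores and Fig. 2 was not available to me, so p=0.04 cannot be reproduced from data. An indirect check is possible. Assume that 0.04 is the day-2 Kruskal-Wallis p, that the pairwise tests are Dunn tests, two-sided, on all 72 patients (26, 24 and 22), and that there are no ties. Each pairwise p gives a z, and each z gives a standardised mean-rank difference d = z × √(1/n₁ + 1/n₂). Setting the acupuncture arm to 0, H = Σ nᵢ(dᵢ − d̄)² on 2 degrees of freedom, where d̄ is the weighted mean of d.

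*Printed values read as raw:*
- z = 2.257 (sham-control) and 2.014 (SOC-control)
- d = 2.257 × √(1/26 + 1/24) = 2.257 × 0.2831 = 0.639, and 2.014 × √(1/26 + 1/22) = 2.014 × 0.2897 = 0.583
- d̄ = (24 × 0.639 + 22 × 0.583)/72 = 0.391
- H = 3.98 + 1.47 + 0.81 = 6.26, so p = 0.044

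*Printed values read as already tripled* (raw 0.008 and 0.0147):
- z = 2.652 and 2.441; d = 0.751 and 0.707; d̄ = 0.466
- H = 5.65 + 1.94 + 1.27 = 8.87 (from unrounded terms), so p = 0.012

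The raw reading agrees with the printed 0.04; the adjusted reading does not.

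**Step 4. How far to trust that check.** I applied the same method to two other results in the section. For dyspnea on day 1 (pairwise 0.031 and 0.014) it gives a three-group p of 0.026 if raw and 0.007 if adjusted, against 0.014 printed. For respiratory rate on day 2 (0.005 and 0.003) it gives 0.003 and 0.0009, against 0.002 printed. Neither reading matches in either case. The sputum check therefore points towards raw values but does not settle the question.

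**The case against.** The strongest reply is that nothing is hidden. The limit to day 2 stands in the very next sentence, with its p-value. The section usually gives a three-group result and then a pairwise breakdown, and the sputum text can be read that way, with day 2 as the day on which the difference first appears. On day 2 both contrasts are reported as significant. Sputum is a secondary outcome, and the document has no discussion or conclusion that builds on it.

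Most of this stands, and it makes the point one of overstatement, not concealment. It does not rescue the summary sentence. That sentence names both controls and a direction, whereas the dyspnea result in the same section is correctly introduced as a difference between the three groups, and the pH result says openly that no head-to-head comparison was significant.

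Two stronger readings are tempting, and the documents support neither.

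- A reader might infer that the post-hoc tests contradict lower sputum than SOC-control on days 3 and 4. They do not. Non-significance in arms of 26 and 22, with no estimate or p-value in the text, leaves the claim unsupported; it does not show that the arms were alike.
- A reader might infer that a difference from sham-control alone reflects unusually high scores in the sham arm. No post-treatment sputum score in the text bears this out, and sham-control versus SOC-control was not significant. The baseline medians (6.0 acupuncture, 6.0 sham-control, 5.0 SOC-control) leave a lower starting level in the SOC arm as another possibility. The text cannot choose between them.

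**Conclusion.** The point holds as one about what may be claimed. A statistical difference in sputum from SOC-control on days 3 and 4 is not supported by the trial's own tests, and the single three-group p of 0.04 cannot supply it. This rests only on the two adjacent sentences and on reading the summary as running to day 4.

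Whether the claim narrows further depends on a fact that the document does not give. If the printed pairwise values are already adjusted, three contrasts against sham-control and one against SOC-control remain. If they are raw, one remains, sham-control on day 3 (0.030), and none against SOC-control. The indirect check favours raw values, but under assumptions about the test, ties and complete data, and it fits neither reading for dyspnea or respiratory rate. It is a reason to ask, not a finding that Bonferroni was left out.

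**What to change.** 1. Report the three-group sputum result as a difference between the three groups, with the day to which p=0.04 belongs.
2. State direction only from the pairwise tests. For each of days 2 to 4 and each pair, give the estimate, confidence interval and Bonferroni-adjusted p, including SOC-control on days 3 and 4. If Fig. 2 already shows some of these, point to it.
3. Say whether the printed pairwise p-values are raw or adjusted, and word the result to match:
   - **Already adjusted:** lower than sham-control on days 2 to 4 and lower than SOC-control on day 2 only; no difference from SOC-control shown on days 3 and 4.
   - **Raw:** after adjustment, lower than sham-control on day 3 only; no sputum difference from SOC-control claimed on any day.

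The second wording must not be skipped: restating the printed results as they stand would itself be wrong if the values are raw. The work is a text change and one table from data already in hand. The price is a less favourable secondary claim.
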